# 7.0 Data and Specimen Banking\*

The electronic data will be managed in an excel file of a local computer drive with frequent electronic backups in a securely encrypted cloud storage service (ShareFile). The stored data will include date of birth, medical record number, assigned sex at birth, BMI, otologic diagnosis, degree of anatomic involvement, bacteria culture results, presenting symptoms, amount and type of drainage, specific site of infection, external ear canal volume estimates, configuration of the external auditory canal, prescribed treatment, treatment outcome, and duration of infection.

All specimens will not be stored longer than necessary to complete analysis and will be discarded through proper DHMC lab protocols.

# 8.0 Sharing of Results with Subjects\*

The subjects will be asked whether they would like to receive the study results, which would be released in the form of a manuscript or journal article over email at the conclusion of the study. Furthermore, a form to share (or not share) any incidental findings and investigational diagnostic tests such as bacterial culture results will be provided as an option to the subject.

#### 9.0 Study Timelines\*

Proposal	AUG	SEP	OCT	NOV	DEC	JAN	FEB	MAR
Timeline								
Funding	Х	Х	Х					
Acquisition								
& IRB								
Process								
Assay		Х	Х	Х	Х			
Development								
Patient					Х	Х	Х	
Recruitment								
& Sample								
Collection								
Statistical						Х	Х	Х
Data								
Analysis								
Concluding							Х	Х
Analysis,								
Article								
Submission								

Subject enrollment is anticipated from December 2021 to January 2022 with subsequent data collection and analysis happening immediately afterwards. The subjects will be followed up with weekly until infection is resolved (for a maximum of 3 months). The study is anticipated to end in December 2021.

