# 1.0 Study Summary

Study Title	Antibiotic concentration after delivery to middle ear for				
	chronic suppurative otitis media				
Study Design	Prospective observational study				
Primary Objective	Investigate the reliability of ciprofloxacin concentration				
	measurements from aspirates of middle ear fluid after self-				
	administration of otic drops in patients with chronic otorrhea				
	and non-intact tympanic membrane				
Secondary	Elucidate the role of antibiotic concentration in varying				
Objective(s)	clinical outcomes in patients with chronic middle ear				
	infections by using antibiotic concentration analysis of				
	aspirates.				
Research	Patients diagnosed with chronic suppurative otitis media				
Intervention(s)/	prescribed with antibiotic drops $(0.3\%$ ciprofloxacin, 0.1%				
Investigational	dexamethasone suspension) will apply drops 1-hour prior to				
Agent(s)	visit. During visit, the ear will be cleaned of any debris and a				
	microscopic aspirate of approximately 100 microliters will				
	be collected with a modified Juhn Tym-Tap device.				
IND/IDE #	N/A				
Study Population	Adults in the community with diagnosed chronic middle ear				
	infection				
Sample Size	N=10				
Study Duration for	An individual participant will be followed on a weekly basis				
individual	until reaching either criteria of complete symptom				
participants	resolution, new treatment prescription, or maximum duration				
	of 3 months				
Study Specific	Chronic suppurative otitis media (CSOM)				
Abbreviations/					
Definitions					

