# 4.0 Study Endpoints\*

The specific aim is to investigate the reliability of accurately measuring the concentration of ciprofloxacin from aspirates of middle ear fluid after self-administration of otic drops in subjects with chronic otorrhea. A secondary aim is to correlate these concentrations with patient factors such as the extent of otorrhea and the anatomy of the ear.

Objective	Study Endpoint	Safety Endpoint
Investigate the reliability of measuring concentration of ciprofloxacin from middle ear aspirates	Precise sampling of a known aspirate volume (100 microliters) and performance of LC-MS/MS ciprofloxacin assay development for middle ear aspirate analysis	
Correlate the concentrations with patient factors	Correlate ciprofloxacin concentration of middle ear aspirate to symptom resolution time, patient demographics, patient anatomy and clinical outcomes (infection resolution).	

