## 13.0 Recruitment Methods

The potential subjects will be recruited in the ENT clinic from July to September 2021 during otology clinic hours. Provider will screen using inclusion-exclusion criteria described above in conjunction with clinical presentation aligned with CSOM diagnosis.

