# **19.0** Provisions to Protect the Privacy Interests of Subjects

The subjects' privacy interests will be conserved in this study as the subject will primarily see the physician and will only be exposed to one more interaction should they give informed consent.

At every encounter between the subject and research team, the subjects will be offered a time to ask questions as well as an email and cell-phone number to call for any forgotten questions.

The research team will have access to the subjects' electronic medical records as well as the master data file stored onto the encrypted cloud storage. The excel data file will only be shared with people directly involved in the data entry and analysis.

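### The enrollment and end dates in Sections 9 and 13 contradict each other, and the charted March finish precedes the 3-month follow-up limit for January enrollees

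*Combined protocol and SAP*

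**What the plan says.** Section 9 (Study Timelines) makes three statements in one paragraph:

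- On enrollment: "Subject enrollment is anticipated from December 2021 to January 2022 with subsequent data collection and analysis happening immediately afterwards".
- On follow-up: "The subjects will be followed up with weekly until infection is resolved (for a maximum of 3 months").
- On the end of the study: "The study is anticipated to end in December 2021".

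The chart above that paragraph runs from August to March without years. It marks recruitment and sample collection in December to February, statistical analysis in January to March, and concluding analysis with article submission in February and March. March is the last column.

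Section 13 (Recruitment Methods) says that subjects will be "recruited in the ENT clinic from July to September 2021".

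Section 1 (Study Summary) agrees with Section 9 on length of follow-up: "An individual participant will be followed on a weekly basis", ending at the first of complete symptom "resolution, new treatment prescription, or maximum duration" of 3 months.

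Section 4 (Study Endpoints) makes follow-up data part of the secondary objective: "Correlate ciprofloxacin concentration of middle ear aspirate to symptom resolution time", and also to clinical outcomes, defined there as infection resolution.

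**The concern.** There are two problems, one of fact and one of consequence.

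The calendar contradicts itself. A study cannot end in December 2021 while enrolling until January 2022, and the Section 13 window closes two months before the Section 9 window opens. Someone running the study cannot tell from the text when enrollment opens, when it closes, or when the study is over.

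The secondary outcomes depend on follow-up that may outlast the charted finish. If the final analysis is done by the end of March, the follow-up available to a slow-resolving subject depends on the date of enrollment. The subjects cut short would be late enrollees who had neither resolved nor been given a new prescription. Those are informative cases for a study asking whether low delivered concentration goes with poor outcome. The only named test is Fisher's exact test (Section 17), which makes no allowance for incomplete follow-up, so a subject cut short would have to be counted as unresolved or left out. With 10 subjects, each is one tenth of the data.

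**Working it through.** **Inputs**

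- Enrollment window: December 2021 to January 2022 (Section 9 text), or July to September 2021 (Section 13).
- Maximum follow-up: 3 months (Sections 1 and 9).
- Stated end: December 2021, taken at its latest as 31 December (Section 9 text).
- Charted finish: March, taken as 31 March 2022. The year is inferred from the Section 9 text, and the last day of the month is the most generous reading.

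**Formula**

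End of maximum follow-up = enrollment date + 3 months. Days available = 31 March 2022 − enrollment date.

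**Step 1. Can the stated December 2021 end be reproduced?**

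From the Section 9 window it cannot. Even the earliest enrollee, on 1 December 2021, reaches 3 months on 1 March 2022, which is 60 days after 31 December. The latest, on 31 January 2022, reaches it on 30 April 2022, which is 120 days after.

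From the Section 13 window it can: 30 September 2021 + 3 months = 30 December 2021. The end date therefore fits Section 13 and not the paragraph in which it stands. Section 25, which plans full-time commitment in July and August, fits the same calendar. The likely explanation, which is an inference, is that Section 13 and the end-date sentence were left over from an earlier timeline.

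**Step 2. Does the charted March finish leave room for 3 months?**

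| Enrolled | + 3 calendar months | + 90 days | Days available by 31 March 2022 |
|---|---|---|---|
| 1 December 2021 | 1 March 2022 | 1 March | 120 |
| 31 December 2021 | 31 March 2022 | 31 March | 90 |
| 1 January 2022 | 1 April 2022 | 1 April | 89 |
| 31 January 2022 | 30 April 2022 | 1 May | 28 + 31 = 59 |
| 28 February 2022 | 28 May 2022 | 29 May | 31 |

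December enrollees can complete follow-up by 31 March. No January enrollee can: the shortfall runs from 1 day (1 January) to 30 days (31 January), or 31 days on a 90-day count.

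**Step 3. Does the reading of 3 months matter?**

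On a 12-week reading (84 days), 6 January + 84 days = 31 March, so only those enrolled after 6 January fall short, by up to 84 − 59 = 25 days. On a 13-week reading (91 days), a 31 December enrollee also misses, by one day. The conflict between the end date and the enrollment window holds on every reading.

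**Step 4. February.**

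The chart's February mark covers recruitment and sample collection together. A 31 January enrollee's aspirate, due 3 to 10 days later, falls on 3 to 10 February, so February may be collection only. The 28 February row above applies only if new enrollment continues through that month.

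**The case against.** The strongest reply is that this is clerical. The December end date looks like stale text, the dates are described as anticipated, and no section stops follow-up in March or sets a data lock. The chart has no follow-up row, and its analysis row already overlaps recruitment, so it is not a data cut-off. Sections 1 and 9 both state the 3-month rule. A team that follows the rule would let the calendar slip and lose nothing. Even on the chart, a 31 January enrollee has 59 days, about eight weekly contacts, after a ten-day course of drops.

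Most of this stands, and it limits the point. It does not remove it. The dates still conflict, and the chart still schedules the concluding analysis and submission before follow-up of January enrollees can be complete. The plan does not say which gives way.

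Three stronger readings are tempting and are not supported:

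- A reader might infer that January enrollees would get no follow-up at all, because the study ends in December. That treats an evidently stale date as operative, against the follow-up rule in the same paragraph.
- A reader might turn the share of enrollment dates that miss the limit into a share of subjects. The documents give no accrual pattern and no rate of resolution or new prescription, so the number affected could be anything from none to all 10.
- A reader might infer from the chart that Section 13 recruits before ethics approval. The chart row combines funding with the IRB process, so its October mark may be funding alone, and the revision history shows review comments being answered by 2 July 2021.

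**Conclusion.** The point holds as an internal inconsistency with a conditional consequence. The contradictions between the Section 9 enrollment window, the Section 9 end date and the Section 13 window are certain on the text.

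The loss of outcome data is not certain. It requires that the charted finish be followed, that the chart's March be March 2022, and that some January enrollees still be unresolved and without a new prescription at that point. Under those conditions, the follow-up lost is at most about one month per subject for the Section 9 window, or about two months if enrollment runs through February.

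The effect is confined to symptom resolution time and infection resolution, which are secondary. Subjects who resolve or receive a new prescription before the cut-off lose nothing. The primary aim, assay reliability, does not depend on follow-up, nor do the analyses of concentration against anatomy and drainage.

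The text should be corrected before enrollment, because correction is cheap and removes the risk entirely.

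**What to change.** - State one enrollment window, the same in Sections 9 and 13, and say whether the chart's February mark includes new enrollment.
- Replace the December 2021 end date with one that follows from that window: last enrollment plus 3 months, plus time for analysis. For a 31 January 2022 close, follow-up ends about 30 April to 1 May 2022. For a 28 February close, it ends about 28 to 29 May.
- State that the final analyses of symptom resolution time and infection resolution are run only after that date, or sooner if every subject has already met a stopping criterion.
- Keep the assay work and the analyses of concentration against anatomy and drainage on the current calendar.

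The cost is wording in two sections and a delay to the final secondary outcome analysis and its submission. The delay beyond 31 March is 30 to 31 days for a 31 January close, or 58 to 59 days for a 28 February close. No subjects, visits or follow-up are added, since up to 3 months is already planned.

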## **10.0 Inclusion and Exclusion Criteria\***

Inclusion criteria include:

- Adult patients greater than or equal to 18 years of age
- Diagnosis of CSOM

#### Exclusion criteria include:

- Atypical presentation of CSOM or atypical anatomy of the ear
- Presence of additional ear pathophysiology beyond CSOM
- Adults unable to consent
- Individuals who are not yet adults (infants, children, teenagers)
- Pregnant women
- Prisoners

• Non-English speaking

# **11.0 Vulnerable Populations\***

This is not applicable to this study.

## 12.0 Local Number of Subjects

Ten subjects will be accrued locally in the ENT clinic on 4F at DHMC in Lebanon, NH.

## 13.0 Recruitment Methods

The potential subjects will be recruited in the ENT clinic from July to September 2021 during otology clinic hours. Provider will screen using inclusion-exclusion criteria described above in conjunction with clinical presentation aligned with CSOM diagnosis.

## 14.0 Withdrawal of Subjects\*

Circumstances for subject withdrawal from research may include non-compliance with prescribed antibiotic regiment or any additional necessary medical intervention beyond that prescribed for CSOM. The study team does not plan to collect survival data from subjects that withdraw from the study. The subject always has the option to voluntarily withdraw from the study.

## 15.0 Risks to Subjects\*

Participation for the subject may cause:

- Mild physical discomfort with an additional study-related sample collection using a Juhn Tym-Tap device
- Psychological stress via social pressure to comply to medication regiment and research protocol
- Time and potential indirect financial expense, especially for subjects who may have higher reliance on hourly wage

# 16.0 Potential Benefits to Subjects\*

The subject may benefit from the additional examination and cleaning 3 to 10 days after the follow up appointment as well as higher social pressure to comply to prescribed medication regiment.

# 17.0 Data Management\* and Confidentiality

Given the small sample size (n=10) and expected variability of results, a Fisher's exact test will be used to describe and compare the measured concentration of ciprofloxacin at the tympanic membrane to subject demographics as well as extent of perforation, amount of aural drainage and treatment outcomes.

The data will be managed on a locally encrypted device in an Excel file while stored on the encrypted cloud storage service called ShareFile. Access will be provided to those on the research team on a need-to-know basis with particular caution to ensure separation of identifiers and data. Any communication in a non-encrypted platform will not contain any protected health information.

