# 2.0 Objectives\*

The purpose of this study is to develop methodology to better understand the potential effect of ototopical concentration on clinical outcomes in patients with chronic middle ear infections. The investigators will do so by measuring antibiotic concentration in aspirates from the middle ear of selected subjects with otorrhea due to Chronic Suppurative Otitis Media (CSOM) who are prescribed and instructed to self-administer ototopical ciprofloxacin.

The primary specific aim of the study team is to investigate the reliability of measuring the concentration of ciprofloxacin from aspirates of middle ear fluid after self-administration of otic drops in subjects with chronic otorrhea. A secondary aim is to correlate these concentrations with subject factors such as the extent of otorrhea and the anatomy of the ear.

The investigators hypothesize that patient self-administration of ciprofloxacin drops results in variable concentrations delivered to the tissue level that are significantly below the in vitro concentration of the prescribed solution and that these concentrations are below the bactericidal concentration of ciprofloxacin-resistant bacteria as determine by our previous work. Additionally, the investigators anticipate that the concentration levels of ciprofloxacin at the level of the tympanic membrane will correlate with specific patient factors and clinical outcomes.

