# 3.0 Background\*

Chronic suppurative otitis media (CSOM) is characterized by chronic inflammation of the middle ear with persistent discharge from a non-intact tympanic membrane. CSOM is notably associated with a significant burden of disease worldwide (1). The most common pathogens are staphylococcus spp., klebsiella spp., pseudomonas aeruginosa, corynebacterium spp, and proteus spp. (2). Topical fluoroquinolones are first line therapy for CSOM and are advantageous as compared to oral or intravenous therapy in that these antibiotics avoid systemic side effects and have the potential to deliver high antibiotic concentrations directly to the middle ear mucosa (3-5). However, because of their widespread use, fluoroquinolone resistance has steadily risen (6-8), making management of CSOM challenging.

A prior study by the study team confirmed 141 patients with ciprofloxacin-resistant otitis media had poor outcomes when using ciprofloxacin drops compared to alternative therapy options (9). Similarly, Jang et al. recovered ciprofloxacin-resistant P. aeruginosa from all patients (n=88) with unremitting CSOM in the context of topical ciprofloxacin therapy in a prospective population of 231 outpatients. Of these 88, over 40% required intravenous antibiotics (10). These findings contradict the previously accepted thought by many practicing otolaryngologists that the high concentrations (3000 mcg/ml) obtained with topical fluoroquinolone antibiotic preparations (3000 mcg/ml) would sufficiently

overcome all bacterial resistance to fluoroquinolones. This belief is based on the fact that minimum inhibitory concentration (MIC) levels are derived from available plasma concentrations. (4,11).

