# 5.0 Study Intervention/Investigational Agent

The standard of care for CSOM involves ototopical quinolone therapy such as ciprofloxacin or ofloxacin. The affected ear is routinely cleaned of any debris, and a Juhn Tym-Tap® device will be used to aspirate fluid for culture samples. The patient will be provided the standard course of treatment, which is a prescription

for antibiotic drops of ciprofloxacin 0.3% and dexamethasone 0.1% suspension with specific written instructions. The frequency of treatment is three times daily for ten days.

For this study, patients who meet inclusion-exclusion criteria will be offered an opportunity to participate by the prescribing provider. Informed consent will be obtained. Enrolled subjects will be asked to return 3 to 10 days after the initial visit. Additionally, the subject will be asked to keep a log of their medication use and to administer the ototopical medication one hour prior to their appointment. During the follow-up appointment, the ear will be cleaned of any wax or purulent debris. A microscopic aspirate (~100 µL) will then be collected of fluid at the level of the non-intact tympanic membrane will be collected using with a modified Juhn Tym-Tap®. This type of sampling of middle ear aspirates is commonly performed in the ENT clinic (performed more than 120 times in the Dartmouth-Hitchcock ENT clinic in the past year). After sampling, the volume of the aspirate will then be precisely measured with a device developed specifically for this study. The color and consistency of the sample will be noted. The sample will then be diluted with a known volume of water to an acceptable volume for the LC-MS/MS assay. Furthermore, other data beyond ciprofloxacin concentration such as otologic diagnosis, bacteria culture results, presenting symptoms, specific site of infection, external ear canal volume estimates (based upon tympanometry and physical exam), configuration of external auditory canal, prescribed treatment, treatment outcome, and duration of infection will be noted for each subject.

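### Section 17.0 plans only Fisher's exact test for a continuous concentration, with no categories and no effect estimate; canal volume and the Section 2.0 hypothesis have no named analysis, and resolution time has no suitable one

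*Combined protocol and SAP*

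**What the plan says.** Section 17.0 holds the whole statistical plan in one sentence. It cites the small sample (n=10) and says that Fisher's "exact test will be used to describe and compare the measured concentration of ciprofloxacin at the tympanic membrane to subject demographics" and goes on "as well as extent of perforation, amount of aural drainage and treatment outcomes". It gives no cut-point, table layout, effect measure or interval.

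Other sections ask for more:

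- Section 2.0: "A secondary aim is to correlate these concentrations with subject factors such as the extent of otorrhea and the anatomy of the ear".
- Section 4.0, second endpoint: "Correlate ciprofloxacin concentration of middle ear aspirate to symptom resolution time, patient demographics, patient anatomy and clinical outcomes (infection resolution".
- Section 2.0, hypothesis: concentrations will be "significantly below the in vitro concentration of the prescribed solution", and "these concentrations are below the bactericidal concentration of ciprofloxacin-resistant bacteria as determine by our previous work". No bactericidal value is given.
- Section 3.0 gives the strength of the drops: "the high concentrations (3000 mcg/ml) obtained with topical fluoroquinolone antibiotic preparations".
- Section 5.0 collects "external ear canal volume estimates (based upon tympanometry and physical exam"; Sections 6.0 and 7.0 list canal volume again.

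Section 6.0 describes the concentration as an LC-MS/MS quantity read from a calibration curve. Section 7.0 stores date of birth and BMI. Under Section 1.0, follow-up ends at symptom resolution, a new prescription or 3 months.

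**The concern.** Fisher's test works on counts in categories. Concentration, age and BMI are continuous, and perforation and drainage have no stated scale, so the sentence cannot be carried out until someone invents the categories. If that happens after the data are in, the analyst's choice of cut can decide whether significance is attainable and can raise the false-positive rate. A p-value alone also does not answer an aim of correlating: with 10 subjects, the size of an association and its uncertainty are the useful output.

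The coverage is also incomplete. Canal volume belongs to the anatomy aim but is missing from Section 17.0, where extent of perforation is the only anatomical variable. Symptom resolution time is not named. The comparison with the two reference concentrations, which opens the Section 2.0 hypothesis, appears nowhere in the analysis.

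**Working it through.** The documents give N=10 without alpha, power, effect size or precision target, so there is no figure of the plan's own to reproduce. Assumed here: two-sided 0.05, distinct values unless stated, and normal data in the simulations.

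**1. Ungrouped data.** With 10 distinct concentrations against a 5/5 factor, every table has probability 1/C(10,5) = 1/252, so Fisher's p is always 1. Grouping is unavoidable.

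**2. Smallest attainable p after a median cut.** For a factor with m subjects in its smaller group, the most extreme table puts all m on one side of the cut. The two-sided p is 2·C(5,m)/C(10,m). For the exact Wilcoxon rank-sum test the minimum is 2/C(10,m).

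| Factor split | Fisher, median cut | Wilcoxon |
|---|---|---|
| 5/5 | 2·1/252 = 0.008 | 2/252 = 0.008 |
| 4/6 | 2·5/210 = 0.048 | 2/210 = 0.010 |
| 3/7 | 2·10/120 = 0.167 | 2/120 = 0.017 |
| 2/8 | 2·10/45 = 0.444 | 2/45 = 0.044 |

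With a median cut and a 3/7 or 2/8 factor, Fisher's test cannot reach 0.05 whatever the data show.

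**3. Continuous factor (age, BMI, canal volume).** Bivariate normal simulation, n=10, Spearman critical value 0.648:

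| True correlation | Spearman | Fisher, both at median | Fisher, best of 81 fixed cut pairs |
|---|---|---|---|
| 0.5 | 26% | 4% | 19% |
| 0.7 | 56% | 11% | 35% |

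**4. Two-level factor (sex, resolved yes/no).** At a 2 SD shift, Wilcoxon power for 5/5, 4/6, 3/7 and 2/8 is 68%, 69%, 59% and 51%. The best fixed Fisher cut gives 66%, 70%, 68% and 51%. Other cuts give 0%: against a 5/5 factor, for example, any cut leaving 3 or fewer subjects on one side.

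**5. False positives.** Any single fixed cut stays within 5%. If both cuts are searched after seeing the data, the rate is about 30% for two continuous variables (about 25% with at least 3 subjects per side). For two-level factors, searching the concentration cut gives 7.9%, 9.5%, 6.7% and 4.4%.

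**6. Section 2.0 hypothesis.** A direct comparison is feasible with 10 subjects.

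- Sign test against 3000 mcg/mL: 2·(1/2)^10 = 0.002 if 10/10 are below; 2·(1+10)/1024 = 0.021 if 9/10; 2·(1+10+45)/1024 = 0.109 if 8/10.
- Median: the interval from the 2nd to the 9th ordered value has exact coverage of at least 1 − 2·(1+10)/1024 = 97.9%.
- Proportion below a fixed value: if 10/10, the exact 95% lower limit is 0.025^(1/10) = 69%.

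**7. Precision of a correlation.** For an observed Spearman r of 0.5, the Bonett-Wright standard error on the z scale is √((1 + 0.5²/2)/7) = 0.401. The interval tanh(0.549 ± 1.96·0.401) is about −0.23 to 0.87.

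**The case against.** The strongest defence is that Fisher's test is exact, holds its level at n=10, and is adequate for an exploratory study once categories are set. Much of that stands. A reader might infer that the test is invalid here; it is not. For two-level factors a well-placed fixed cut matches the rank-sum test, so fixing the cut in advance and adding an odds ratio would largely suffice. The 11% power in step 3 is partly discreteness: the 5/5 by 5/5 table has a true size of 2/252 = 0.8%, and moving one cut to 4/6 raises power to about 31%. But small numbers justify exact methods in general, and the exact rank methods need no cut.

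Three stronger readings are tempting, and the documents do not support them.

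- *Resolution time has no analysis at all.* The treatment outcomes in Section 17.0 may include it. What can be said is that it is not named, and that Fisher's test does not suit a time limited by follow-up.
- *Section 2.0 implies that nearly everyone falls below the bactericidal level, so Fisher's test must fail.* With 9 or 10 of 10 on one side, p indeed cannot go below 0.10 for any two-level factor. But Section 2.0 gives neither a proportion nor a value, and Section 17.0 does not say the cut would be placed there.
- *The false-positive rate will be 30%.* That needs a search over all cut pairs, which nothing in the documents describes.

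Rank methods have limits too. The ofloxacin study cited in Section 3.0 had five patients with undetectable levels beside 11 with measurable ones. If 3 of 10 subjects tied at the bottom (an illustration), a 2/8 factor with both of its subjects among them has probability C(3,2)/C(10,2) = 0.067, so 0.044 is out of reach in that direction. The sign test against 3000 mcg/mL may also be close to a foregone conclusion, since drops mixing with ear fluid would be diluted; the size of the shortfall is more informative.

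**Conclusion.** The concern holds and should be fixed. Three things follow from the text without assumptions: no categories are defined, no correlation or effect estimate is planned, and neither canal volume nor the comparison with the two reference concentrations has a named analysis.

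The size of the loss rests on the assumed 0.05 level, normal data and true associations. It is substantial for continuous factors (56% against 11% to 35% at a correlation of 0.7) and absent for two-level factors if the cut is well placed. The 30% false-positive figure is a worst case.

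A reader might infer that the whole study is undermined. It is not: the primary aim, reliability of the concentration measurement, does not depend on this sentence. Only the secondary aim and the Section 2.0 hypothesis are affected, and the associations stay exploratory under any method.

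**What to change.** Replace the Fisher sentence in Section 17.0 with the following.

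1. **Continuous or graded factors** (age, BMI, canal volume, and perforation and drainage on scales fixed in advance): Spearman correlation with exact permutation p and 95% CI.
2. **Two-level factors:** exact Wilcoxon rank-sum test, ties handled by permutation. Give a Hodges-Lehmann estimate and CI when all values are quantifiable, otherwise a rank-based effect such as the probability of superiority.
3. **Undetectable concentrations:** tied lowest rank, not missing. Because samples are diluted (Section 5.0), record the dilution-adjusted detection limit for each sample, and add a sensitivity analysis if limits differ.
4. **Fisher's test:** only for truly categorical pairs or a concentration threshold fixed in advance, with odds ratio and exact CI. Report counts only if 9 or 10 subjects fall on one side.
5. **Resolution time:** a rank analysis with unresolved or newly treated subjects ranked longest. Retain their outcome data where available, and count and report withdrawals under Section 14.0. Use censoring only as a sensitivity analysis, since censoring at new treatment may be informative.
6. **Section 2.0 hypothesis:** median concentration as a percentage of 3000 mcg/mL with an exact CI (the sign test may accompany it), and the proportion below a bactericidal value fixed in advance from the team's earlier work, with exact 95% CI.

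Label all association results exploratory.

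The cost is about a paragraph of wording, the grading scales, the bactericidal value and a detection limit noted per sample. No extra subjects or visits are needed. Intervals stay wide at n=10, and the report should say so.
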